7.1.3. Analyses for Continuous Data

Continuous variables will be summarized using descriptive statistics (eg, n , mean, median, SD, minimum, maximum, and first and third quartiles). For the analyses of change from Baseline, the mean at Baseline will be calculated for all patients with at least one post-Baseline value by treatment group. Additionally, the mean will also be calculated for each visit, including only the patients who are in the analysis who have data for that visit by treatment group.

7.1.4. Analyses for Time to Event Data

Time-to-event endpoints will be summarized using the Kaplan-Meier method. The median, quartiles, and probabilities of an event at particular time points will be estimated by the Kaplan-Meier method.

Confidence interval for the Kaplan-Meier estimation is calculated using the exponential Greenwood formula via log-log transformation of the survival function.

The variance of the treatment difference will be calculated using the following formula:

$$V[\widehat{S}_R(t) - \widehat{S}_L(t)] = \widehat{V}[\widehat{S}_R(t)] + \widehat{V}[\widehat{S}_L(t)];$$

where each of the component of the variance of the Kaplan-Meier estimate will be calculated using Greenwood's formula:

$$\hat{V}[\hat{S}(t)] = \hat{S}(t)^2 \sum_{t_i \leq t} \frac{d_i}{n_i(n_i - d_i)}$$

where n_i denotes the number of patients at risk at time t_i , and d_i denotes the number of events observed at time t_i .

The 95% CI of the treatment difference will be calculated using a log-log transformation of the difference in survival function, as follows:

$$[(\widehat{S}_R(t) - \widehat{S}_L(t))^{\exp(1.96 \hat{\tau}(t))}, (\widehat{S}_R(t) - \widehat{S}_L(t))^{\exp(-1.96 \hat{\tau}(t))}]$$

$$\text{where } \hat{\tau}^2(t) = \frac{\hat{V}[\widehat{S}_R(t) - \widehat{S}_L(t)]}{\{[\widehat{S}_R(t) - \widehat{S}_L(t)] \log[\widehat{S}_R(t) - \widehat{S}_L(t)]\}^2}.$$

A stratified log-rank test will be used to compare each relugolix arm to placebo. Randomization stratification factors will be used to stratify inferential testing.

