2.2. Sample Size Considerations

2.2.1. Sample Size Justifications for Primary Efficacy Endpoint

The following assumptions were used to determine the sample size for this study:

- 2-sided type I error rate: 0.05
- Randomization: 1:1:1
- Responder rate for placebo group: 25%
- Difference in responder rates between the relugolix + E2/NETA group and the placebo group: 30%
- Dropout rate: ~20%

With the assumption of a dropout rate of 20%, approximately 130 women in the relugolix + E2/NETA group and 130 women in the placebo group will provide at least 99% power at a 2-sided 0.05 significance level to detect a 30% difference in responder rates between relugolix + E2/NETA group and the placebo group for the primary endpoint. With an additional 130 women in the relugolix + delayed E2/NETA group, the total sample size will be approximately 390 women.

The assumed responder rate of 25% for the placebo group is within the range of responder rates observed from similar phase 3 trials in uterine fibroids (Stewart, 2017). The sample size and power calculations are based on a chi-squared test.

2.2.2. Sample Size Justifications for Percent Change in Bone Mineral Density at 12 Weeks

A pooled analysis of the percent change in BMD at 12 weeks using data from both phase 3 studies is described separately in the statistical analysis plan for the Integrated Summary of Safety. The results of this pooled analysis comparing the relugolix + E2/NETA group with the relugolix + delayed E2/NETA group will be presented in the Integrated Summary of Safety and will not be included in the CSRs for these studies.

For the comparison of the relugolix + E2/NETA group with the relugolix + delayed E2/NETA group with respect to the percent change in BMD from Baseline to Week 12 at the lumbar spine (L1–L4), approximately 260 women in the relugolix + E2/NETA group (pooled between the LIBERTY 1 and LIBERTY 2 studies) and 260 women in the relugolix + delayed E2/NETA (pooled) will provide at least 90% power at a 2-sided 0.05 significance level to detect a 1.25% absolute treatment difference, assuming a standard deviation of 4% and up to 15% dropout rate for each treatment group. Power calculations for this BMD comparison are based on a two-sample t-test.

Sample size and power calculations were performed using the software package *nQuery* 4.0 (Statistical Solutions Ltd.).

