^a The safety follow-up visit window will be restricted to assessments prior to the date of initiation of another investigational agent or hormonal therapy affecting the hypothalamic-pituitary-gonadal axis or surgical intervention for uterine fibroids

Table 4: Visit Windows for Week 24 Assessments (Transvaginal Ultrasound, Endometrial Biopsy, EQ-5D-5L)

Visit	Start Day	Target Day	End Day
Week 24	128	169	196
Safety Follow-up ^a	Date of last dose + 7 days	Date of last dose + 30 days	Date of last dose + 60 days

Abbreviations: EQ-5D-5L, European Quality of Life Five-Domain Five-Level.

^a The safety follow-up visit window will be restricted to assessments prior to the date of initiation of another investigational agent or hormonal therapy affecting the hypothalamic-pituitary-gonadal axis or surgical intervention for uterine fibroids.

Table 5: Time Window for eDiary and Feminine Product Collection

Visit	Feminine Product Collection Visit Date ^{a,b}	Time Window ^a
Week 4	X ₁	(Date of Study Day 1) - < X ₁
Week 8	X ₂	(X ₁ +1) - ≤ X ₂
Week 12	X ₃	(X ₂ +1) - ≤ X ₃
Week 16	X ₄	(X ₃ +1) - ≤ X ₄
Week 20	X ₅	(X ₄ +1) - ≤ X ₅
Week 24	X ₆	(X ₅ +1) - ≤ X ₆
Week 24/EOT	X _{Last} ^c	(Previous Feminine Product Returned Visit +1)] - ≤ X _{Last}

^a If feminine products are collected at more than 1 visit within a given visit window (Table 2), the last feminine product collection date will be used to define the time window. If the patient missed the previous visit, a planned study visit date will be used to calculate the window.

^b In the absence of feminine product collection due to amenorrhea the visit date when amenorrhea was reported will be used.

^c Date of last non-missing feminine product collection within the interval from (last dose date - 35) to (last dose date + 7 days) (see Section 7.3.3).

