7.2. Multiplicity Adjustment

The primary and the ranked secondary efficacy analyses will be performed at an overall alpha level of 0.05 (two-sided) comparing relugolix + E2/NETA (Group A) with placebo (Group C). A test will be deemed statistically significant if the two-sided p-value rounded to four decimal places is < 0.05. A gate-keeping testing procedure will be applied to maintain the family-wise type I error rate for the testing of primary and ranked secondary endpoints (see Section 7.4.1 for details).

Comparative statistics (p-values, 95% CIs for differences) will be provided for the treatment comparison of relugolix + E2/NETA with placebo for all other secondary efficacy endpoints. A treatment comparison of relugolix + delayed E2/NETA (Group B) with placebo will be performed only for the primary efficacy endpoint. There will be no statistical testing for treatment differences between the relugolix groups (Group A versus Group B) for any efficacy endpoints. The relugolix + E2/NETA group and relugolix + delayed E2/NETA group will be compared for the following safety endpoints: percent change from Baseline to Week 12 in BMD and incidence of vasomotor symptoms by 12 weeks (see Section 9.3.5 and Section 9.1.7, respectively). The above comparative analyses are not part of the gate-keeping testing procedure for label claims. p-values for primary and key secondary endpoints were adjusted for multiplicity. All other p-values are provided at a nominal level of 0.05.

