To ensure collection of all feminine products used during that menstrual cycle, an interval of up to 35 days for measurement of the primary endpoint was selected to accommodate women who continue to have cyclic bleeding on study treatment and whose natural cycle was at the upper end of the normal cycle duration range. This method is consistent with that used during screening for collection of feminine products. Specifically, the feminine product collection interval at Week 24/EOT is driven by types of bleeding patterns experienced by the patients, as described below:

- For patients who continue to have cyclic bleeding, the length of the interval depends on the duration of the patient's natural cycle; this is consistent with the way the Baseline MBL volume was determined (eg, the interval ranging from approximately 21 to 35 days);
- Patients who report irregular, non-cyclic bleeding are instructed to collect and return all feminine product used between study visits, up to 35 days, as per the schedule of events;
- For patients who report amenorrhea on the feminine production collection eCRF page, an interval of last 35 days of treatment will be reviewed to ensure that reported amenorrhea is not due to incomplete collection.

For patients who are in the midst of an episode of cyclic bleeding at the time of the Week 24/EOT visit, the visit window may be extended up to 7 days after the last dose of study drug to ensure patients return all used feminine products over that bleeding episode.

Per protocol, all used feminine products are to be collected at each visit and returned for analysis using the alkaline hematin method. For patients who continue to have menstrual bleeding, study visits are timed such that the feminine products used in the entire menstrual bleeding cycle are collected in one container provided at each visit.

MBL Volume at Week 24/EOT

MBL volume at Week 24/EOT is defined as the MBL volume obtained from the feminine product returned over the Week 24/EOT feminine product collection interval, as described above. The MBL volume at Week 24/EOT will be used to derive the primary efficacy endpoint.

If a patient did not return feminine product over the last 35 days of treatment and reported amenorrhea on the feminine product return eCRF page, she will be considered as amenorrhoeic and her MBL volume will be assigned as 0 mL.

Feminine Product Return Rate at Week 24/EOT

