7.4.2. Other Secondary Efficacy and Exploratory Endpoints

The following describes the analysis methods for other secondary efficacy endpoints and exploratory endpoints. There are three types of analyses corresponding to the three types of endpoints (time-to-event, continuous and binary) (see [Appendix 1](#) for details).

Time-to-Event Endpoint

For time to achieving an MBL volume of < 80 mL AND at least a 50% reduction from Baseline MBL volume (as an event), time to event will be defined as weeks from date of first dose of study drug to response (event) based on the MBL volume as assessed by the alkaline hematin method. The missing data handling rules described in Section [7.3.5](#) for deriving responder status at Week 24/EOT will be applied similarly at Weeks 8, 12, 16, and 20. Patients without an event will be censored at the last assessment date prior to the last dose of the study drug.

Kaplan-Meier methods will be used to describe the time to event distributions. A log-rank test stratified by the randomization stratification factors using the proportional hazard model (p-value from score test) will be used to compare relugolix + E2/NETA to placebo. Randomization stratification factors will be used to stratify inferential testing.

Continuous Endpoints

For endpoints evaluating the change (absolute or percent change) from Baseline to Week 24, treatment comparisons will be performed using a mixed model repeated measures approach with treatment, randomization stratification factors, visit, and treatment by visit interactions included as fixed effects. The Baseline value will be included as a covariate, and an unstructured variance-covariance matrix will be assumed. Calculation of the dependent variable (change from Baseline) for each patient at each visit will be calculated based on the visit windows specified in Section [4.3.5](#). Based on this model, the least squares mean at Week 24 will be compared between treatment groups and summarized along with the corresponding 95% CIs for treatment difference. In addition, summary statistics (mean change or mean % change) will be graphically presented as appropriate.

Binary Endpoints

For endpoints evaluating proportions, treatment comparisons will be performed using a stratified Cochran-Mantel-Haenszel test as appropriate with the randomization stratification factors as strata. Point estimates and 2-sided 95% CIs for treatment differences in proportions will be provided.

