APPENDIX 1. SUMMARY OF SECONDARY ENDPOINT ANALYSES

Secondary Endpoints	Analysis Population	Statistical Method/Test	Declare Statistical Significance ^a	Time Points of Summary	Summary Statistics
Key Secondary Efficacy Endpoints with Alpha Protection					
Proportion of women who achieve amenorrhea over the last 35 days of treatment	mITT	Cochran-Mantel-Haenszel test	P < 0.05	Week 24	Frequency and percentages
% change from Baseline to Week 24 in MBL volume	mITT	Mixed-effects model	P < 0.05	Week 24	LS means for % change
Proportion of women with a hemoglobin ≤ 10.5 g/dL at Baseline who achieve an increase of > 2 g/dL from Baseline at Week 24	Subset of mITT	Cochran-Mantel-Haenszel test	P < 0.05	Week 24	Frequency and percentages
Change from Baseline to Week 24 in the UFS-QoL Bleeding and Pelvic Discomfort Scale score, a sub-scale of the UFS-QoL Symptom Severity Scale	mITT	Mixed-effects model	P < 0.05	Week 24	LS means for change
Proportion of patients with a maximum NRS score ≤ 1 during the 35 days before the last dose of study drug in the subset of women with a maximum NRS score ≥ 4 for pain associated with uterine fibroids during the 35 days prior to randomization	Subset of mITT	Cochran-Mantel-Haenszel test	P < 0.05	Week 24/EOT	Frequency and percentages
% change from Baseline to Week 24 in uterine fibroid volume	mITT	ANCOVA model	P < 0.05	Week 24	LS means for % change
% change from Baseline to Week 24 in uterine volume	mITT	ANCOVA model	P < 0.05	Week 24	LS means for % change
Other Secondary Efficacy Endpoints					
Time to achieve MBL volume of < 80 mL AND at least a 50% reduction from Baseline MBL volume as measured by the alkaline hematin method	mITT	Log-rank test/KM method	P < 0.05	Monthly	KM estimates at Week 12 and 24, KM plots, median time to response
Time to achieve amenorrhea	mITT	Log-rank test/KM method	P < 0.05	Monthly	KM plots, median time to response

Secondary Endpoints	Analysis Population	Statistical Method/Test	Declare Statistical Significance ^a	Time Points of Summary	Summary Statistics
Time to sustained amenorrhea	mITT	Log-rank test/KM method	P < 0.05	Monthly	KM plots, median time to response
Proportion of women in the relugolix Group A versus the placebo Group C who achieve an MBL volume of < 80 mL AND at least a 50% reduction from Baseline MBL volume at Week 4, Week 12, Week 16, and Week 20	mITT	No comparison		at Week 4, Week 12, Week 16, and Week 20	Descriptive

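### The confidence interval for the Kaplan-Meier difference is undefined when relugolix works and can never contain zero; separately, the censoring rule can inflate Week 24 time-to-response estimates

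*SAP*

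**What the plan says.** Section 7.1.4 first deals with each arm's own curve: "Confidence interval for the Kaplan-Meier estimation is calculated using the exponential Greenwood formula via log-log transformation of the survival function". It then gives the variance of the difference as the sum of the two Greenwood variances, which is standard. The next step is the problem: "The 95% CI of the treatment difference will be calculated using a log-log transformation of the difference in survival function". The printed limits raise S_R(t) − S_L(t) to the powers exp(±1.96 τ), and the logarithm of S_R(t) − S_L(t) appears in the denominator of τ. The subscript L matches no arm of this trial; the comparator is placebo.

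Section 7.2 commits to intervals of this kind for all other secondary efficacy endpoints: "Comparative statistics (p-values, 95% CIs for differences) will be provided for the treatment comparison of relugolix + E2/NETA with placebo". For time to menstrual blood loss (MBL) response, Appendix 1 lists "KM estimates at Week 12 and 24, KM plots, median time to response".

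On censoring for that endpoint, section 7.4.2 says: "Patients without an event will be censored at the last assessment date prior to the last dose of the study drug". The final collection need not precede the last dose. Table 5, note c, in section 4.3.5 defines it as "Date of last non-missing feminine product collection within the interval from (last dose date - 35) to (last dose date + 7 days". Section 7.3.3 adds that, for women in the middle of a cyclic bleed at that visit, "the visit window may be extended up to 7 days after the last dose of study drug".

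**The concern.** **The interval.** The log-log transform keeps limits inside (0, 1), which is what one survival probability needs. A difference of two survival probabilities lies in (−1, 1) and may be zero or negative. Here the event is favourable, so S is the probability of not yet having responded, and an effective drug makes S_R − S_placebo negative. The formula then fails exactly where the trial expects to be. Reversing the order makes it computable for a beneficial effect, but forces an interval that excludes zero, so it would look significant at any positive difference. A programmer who notices this must choose a replacement that the SAP does not specify.

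**The censoring rule.** Events carry no limit relative to the last dose, but censoring does. A non-responder whose final collection falls on or after the last dose loses that result and leaves the risk set at her previous assessment. A woman who first responds at the same collection counts as an event. The Week 24 risk set is therefore depleted of non-responders only, and the estimated cumulative response at Week 24 can move upward. The women offered the post-dose extension are still bleeding cyclically, so they are plausibly non-responders.

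**Working it through.** The SAP states no figure for either rule, so there is none to reproduce.

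**Inputs from section 2.2.1:** placebo response 25% ("Responder rate for placebo group: 25" per cent), a 30-point difference (so 55% on relugolix + E2/NETA), and 130 women per arm. Without censoring, the Greenwood variance of one arm is S(1 − S)/n.

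**1. Interval at the planning rates**
- D = S_R − S_P = 0.45 − 0.75 = −0.30. Neither log(D) nor a non-integer power of D exists, so there is no interval.
- Sign reversed, D = 0.30:
  - SE = √(0.45×0.55/130 + 0.75×0.25/130) = 0.0578
  - τ = 0.0578/(0.30 × |ln 0.30|) = 0.160, and 1.96 τ = 0.314
  - limits 0.30^exp(0.314) = 0.192 and 0.30^exp(−0.314) = 0.415
- Linear Greenwood: 0.30 ± 1.96 × 0.0578 = 0.187 to 0.413.

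**2. Why zero is never included.** For any D in (0, 1) and any positive exponent, D raised to that exponent lies strictly in (0, 1). Both limits are therefore always positive.

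**3. A small difference (assumed 30% against 25%, sign reversed).** D = 0.05 and SE = 0.0553. The printed formula gives 0.002 to 0.234; the linear interval is −0.058 to 0.158.

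**4. No true difference (25% in both arms, exact over two binomials with n = 130)**

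| Outcome | Probability |
|---|---|
| S_R − S_P ≤ 0: printed interval undefined | 0.529 |
| S_R − S_P > 0: printed interval exists and excludes zero | 0.471 |
| Linear interval contains zero | 0.948 |

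**5. Censoring.** Assume a true Week 24 placebo response of 25%, no dropout, and all Week 24 assessments tied at one time. Let q = 0.75 be the non-responders, e the proportion of women first responding at Week 24, and f the share of non-responders whose Week 24 assessment precedes the last dose. Then S(20) = 0.75 + e, and under the rule as written

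S(24) = S(20) × f q/(e + f q).

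For f = 0.10 and e = 0.02: 0.77 × 0.075/0.095 = 0.608, an estimated response of 39.2%.

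| f | e = 1% | e = 2% | e = 4% |
|---|---|---|---|
| 0.10 | 32.9% | 39.2% | 48.5% |
| 0.25 | 27.8% | 30.4% | 34.9% |
| 0.50 | 26.0% | 26.9% | 28.6% |
| 1 | 25.0% | 25.0% | 25.0% |

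If f = 0 and at least one woman in the arm first responds at Week 24, the estimate reaches 100%. Neither e nor f is in the SAP, so the table is a range of assumptions and not a prediction.

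**The case against.** **The interval has limited reach.** Appendix 1 asks for Kaplan-Meier estimates, plots and medians, not a difference; testing is by stratified log-rank; and these endpoints are outside the gate-keeping sequence. All of that is true and limits the consequence. But 7.1.4 says the interval will be calculated and 7.2 promises intervals for differences, so it is part of the plan.

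**The sign can be rescued.** Section 7.1.4 also speaks of event probabilities. On that scale, or with the order swapped, the interval exists and at the planning rates is practically the linear one. At 45% against 25% it is 0.101 to 0.323, against 0.087 to 0.313. The two intervals disagree about zero only at about 35% against 25% or less. This is fair as to where the harm lies, but it does not cure an interval that cannot contain zero.

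**The censoring bias rests on unknowns.** Whether the last dose precedes, coincides with or follows the final collection is for the protocol, which is not at hand; at f = 1 there is no bias. The tied-visit assumption also matters. With collection dates spread over ±7 days and the curve read at day 168, f = 0.10 gives 30.4%, 33.6% and 38.9% for e = 1%, 2% and 4%, lower than in the table. The size depends on the read-out day and is not consistently smaller, and the direction holds whenever a material share of non-responders lose their final assessment. What stands is that the magnitude is uncertain; the asymmetry itself is in the text.

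**Conclusion.** Both parts hold. The interval defect is algebraic and needs no outside figure: as printed there is no interval when relugolix does better, and with the sign reversed zero is excluded at every positive difference. The practical damage falls on small differences; at the planned 30 points the sign-reversed and linear intervals nearly agree.

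The censoring rule can bias the Week 24 cumulative probability of response upward. A true 25% appears as 33–49%, 28–35% or 26–29% if 10%, 25% or 50% of non-responders are assessed before the last dose, assuming 1% to 4% of women first respond at Week 24, no dropout and tied visits. Week 12 estimates are essentially untouched among completers; a median, if affected, would move earlier.

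Primary and key secondary inference use neither rule. The log-rank test does not use the interval, and in simulation its power and type I error barely moved under the censoring rule. Time to amenorrhea (7.4.3) escapes the Week 24 bias because its events are dated back to an earlier collection. This should be fixed, but it does not threaten the trial's main conclusions.

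**What to change.** - **Section 7.1.4:** replace the log-log interval for the difference by the linear Greenwood interval, D ± 1.96 √(V_R + V_P), using the variance already given there. Label the arms R (relugolix) and P (placebo) and state the direction of D. At the planning rates this gives −0.300 (−0.413 to −0.187); with S = 0.75 in both arms it gives 0 (−0.105 to 0.105). Keep the log-log interval for each arm's own curve.
- **Section 7.4.2:** censor women without an event at their last MBL assessment through Week 24/EOT, including a collection up to 7 days after the last dose. In the tied-visit, no-dropout example, the Week 24 estimate then returns to 25%.
- **Section 7.4.3:** no change is needed on this ground.

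The cost is one formula, one sentence and a small program change, with no additional data.
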